# 15.0 RESEARCH PARTICIPANT REGISTRATION AND RANDOMIZATION PROCEDURES

## 15.1 Research Participant Registration

Confirm eligibility as defined in the section entitled Inclusion/Exclusion Criteria. Obtain informed consent, by following procedures defined in section entitled Informed Consent Procedures. During the registration process registering individuals will be required to complete a protocol specific Eligibility Checklist. The individual signing the Eligibility Checklist is confirming whether or not the participant is eligible to enroll in the study. Study staff is responsible for ensuring that all institutional requirements necessary to enroll a participant to the study have been completed. See related Clinical Research Policy and Procedure #401 (Protocol Participant Registration).

#### 15.2 Randomization

Patients will be randomized to the standard of care therapy arm or the early, upfront RT followed by standard of care therapy arm. For patients enrolled, immediately after consent is obtained, the CRC at MSKCC will register participants in the Clinical Trial Management System (CTMS). Once the participant's eligibility is established, the registration will be finalized and the participants will be randomized using the Clinical Research Database (CRDB). Randomization will be accomplished by the method of random permuted block, and will be stratified by disease histology and planned standard of care. After

Page **23** of **30** Version: 2/26/16

treatment arm is determined by randomization, the CRCs will notify physicians at MSKCC of the treatment arm within 24 hours of randomization. All data will be collected and analyzed at MSKCC.

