# 8.0 PRETREATMENT EVALUATION

The following tests must be completed prior to enrollment unless otherwise specified:

Prior to study entry (randomization):

patients approached (if applicable).

• Standard of care biopsy proving malignancy, with clinical documentation consistent with metastatic disease, per physician discretion.

Within 6 weeks (42 days) of study entry (randomization):

- CT CAP, FDG-PET/CT scan, MRI Total Spine or NaF-PET can be used, imaging study is at the discretion of the treating physician.
- Other local imaging studies that include the target lesion(s) can also be used as baseline imaging at the discretion of the treating physician.

Within 4 weeks (28 days) of study entry (randomization):

- CBC with differential
- Comprehensive metabolic panel (CMP=Na, K, Cl, CO2, BUN, Creatine, Ca, Glucose, total protein, albumin, alk phos, total bilirubin, AST and ALT).
- Complete medical history including current medications, comorbidities and performance status
- Physical exam including weight, height and vital signs (O2 saturation, blood pressure, heart rate, respiratory rate, and temperature).
- BPI short form and EQ-5D-5L
- Lesion Identification Worksheet should be completed by physicians

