<sup>3 Patient's height is not needed at follow ups and SRE.

<sup>4 All assessments following an SRE are optional, but highly recommended

<sup>5 Baseline imaging can be obtained within 6 weeks of study entry

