## 14.0 BIOSTATISTICS

The primary objective of this study is to compare the rate of skeletal related events (SRE) from the date of randomization to death or 12 months, whichever occurs first, between patients who received standard of care versus upfront, early palliative RT to high-risk bone metastases. We expect 60-80% of the enrolled patients can be followed for 1 year. An SRE is defined as pathological fractures, spinal cord compression, or palliative radiotherapy and orthopedic surgery for bone pain. Data suggest that the event rate is around 60% in the standard of care arm . In our institutional experience, 75% of inpatient radiation consultation led to palliative radiation for painful bone

metastasis, an SRE. Furthermore, 61% of these lesions were diagnosed at least 4 months prior to undergoing RT. We believe 60% estimated event rate at 1-year is a conservative estimate.

The primary endpoint is a binary variable and the rate refers to proportion and is defined as the number of lesions that had SRE divided by the total number of target lesions. This analysis is lesion-based so an SRE (or no SRE) at one site does not affect the status of other sites from the same patient. We estimate that the investigational arm has the event rate around 30%. Radiation therapy is extremely effective in alleviating pain due to bone metastases with 70-80% pain control. By preventing the development of significant bone pain, which often leads to SREs, RT can effectively reduce SREs, To this end we will analyze at least 66 patients with valid SRE endpoint (randomized 1:1 to each arm) to achieve >80% power in detecting such a difference using a two-sample, one-sided proportion test with alpha<0.05. Since patients who withdraw before the endpoint can be evaluated will not be included in the analysis (i.e., it will NOT be an intent-to-treat analysis) we will over-accrue to account for withdrawals to ensure a minimum of 33 patients in each arm (subject to stratification, see Section 15.2) who can contribute the analyzable endpoint of SRE. We believe an additional 10% would be sufficient so totally we expect to randomize 74 patients. A small portion of patients (<15%) may have multiple lesions, in which case they will be treated as independent analysis units. In other words, the eventual effect sample size may be slightly higher than 66 because this objective will be analyzed per lesion.

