Palliative radiation therapy is a well-established, frequently used treatment for patients with metastatic disease. It is often the standard of care for patients with symptomatic metastatic lesion. It is extremely unlikely to be more toxic or cause earlier deaths.

We expect to enroll all 74 patients within 2 years.

Secondary objectives will be analyzed per patient. Unless otherwise specified, all endpoints are defined within the time window from the date of randomization to death or 12 months, whichever occurs first.

To compare the number of hospitalizations related to SREs between standard of care and upfront, early palliative RT arms we will employ a Wilcoxon rank sum test.

To compare quality of life between standard of care and RT arms, using the Brief Pain Inventory (BPI) and EuroQol Group EQ-5D-5L forms, we will test the difference (between the two arms) of the survey results at the following time points: 3 months, 6 months, 12 months and optionally but recommended within one week of any SRE. The individual quantitative scores derived from the BPI, and the utility scores as well as the overall health scores derived from EQ-5D-5L, will be summarized at these assessment times using descriptive statistics (means and standard deviations, medians and quartiles). Differences between the two arms in terms of these quantitative scores at various time points of interest will be evaluated for both statistical and clinical significance using Wilcoxon rank

Page **22** of **30** Version: 2/26/16

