sum tests and established minimally important differences (MIDs) for the various measures, respectively. For scale scores with no established MIDs, the "half standard deviation" rule will be applied (i.e., differences of a half standard deviation will be considered clinically significant). At the conclusion of the study data at each time point will be presented, the number of patients in each group at a given time point will be documented, and the mean EQ-5D-5L and BPI scores for each group will be plotted over time and longitudinal pattern will be examined with the possibility of proposing more complicated regression methods such as the linear mixed models. The categorical answers (e.g., YES vs NO) from EQ-5D-5L will be compared between the two arms using Fisher"s test at each time point as well and odds ratios together with confidence intervals will be computed. Other non-quantifiable answers (e.g., treatment receiving for pain) will be summarized descriptively. For the last question in BPI, the score for pain interference on the BPI Short Form is the mean of the 7 interference questions as long as at least 4 are completed.

For comparing pain-free survival and overall survival between the two arms, both of which are time to event endpoint (time from randomization to start of opioids or death which is not necessarily within 12 months from randomization), we will use log-rank test.

To evaluate CTCAE v4 toxicity events in the upfront RT arms, we will tabulate all toxicities and summarize the CTCAE v4.03 scores and present descriptive statistics. This will be done at 3 months, 6 months, and 12 months from randomization.

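### The planned tests use neither the randomisation strata nor the baseline BPI and EQ-5D-5L scores, which costs power, and one listed questionnaire test compares the arms only among patients who had an SRE

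*Combined protocol and SAP*

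**What the plan says.** - **Strata.** Under Section 15.2, permuted-block randomisation "will be stratified by disease histology and planned standard of care". The number of levels and the block size are not given.
- **Committed tests (Section 14.0).** The primary analysis is a one-sided two-sample proportion test. Hospitalisations and questionnaire scores get Wilcoxon rank sum tests, categorical EQ-5D-5L answers get Fisher's test, and pain-free and overall survival get log-rank tests. None is described as stratified or adjusted. The section's one reference to stratification qualifies the number of patients per arm, not the test.
- **Baseline scores.** Section 8.0 lists "BPI short form and EQ-5D-5L" among the assessments due within 28 days before randomisation, and Sections 4.2.3 and 4.2.4 confirm this for both arms.
- **Questionnaire comparisons.** Section 14.0 tests the arms at "3 months, 6 months, 12 months and optionally but recommended within one week of any SRE". Differences are "evaluated for both statistical and clinical significance using Wilcoxon rank" sum tests and minimally important differences. Where a scale has no established one, "differences of a half standard deviation will be considered clinically significant". No change score or baseline covariate is named. Modelling is mentioned only as plots "with the possibility of proposing more complicated regression methods such as the linear mixed models".
- **At-SRE forms.** Footnote 4 to the Section 10.0 schedule reads "All assessments following an SRE are optional, but highly recommended".

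**The concern.** These are three separate points of unequal weight.

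1. **At-SRE comparison (validity).** A patient enters this comparison only by having the event that RT is meant to prevent, and then only if the optional form is completed. If RT works, the RT patients who still have an SRE are a more selected, higher-risk group than the control patients who have one. A difference in pain or utility could then reflect who is in the subset and not what RT did. A reader would still take the p-value as a treatment effect.
2. **Baseline scores (efficiency).** Pain-related quality of life is a stated secondary objective. Leaving out a baseline value that every patient supplies gives away precision on endpoints for which the trial is already small.
3. **Strata (efficiency).** Section 3.0 cites one-year SRE rates near 50% in prostate cancer and near 90% in renal cell carcinoma, so histology may well be prognostic. If it is, an unstratified test after stratified randomisation is conservative. The plan has no power to spare, as the first calculation below shows.

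**Working it through.** **The plan's own figure.** Inputs from Section 14.0: 60% vs 30%, one-sided 5%, 80% power.

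n per arm = [1.645·√(2·0.45·0.55) + 0.842·√(0.6·0.4 + 0.3·0.7)]² / 0.30² = (1.157 + 0.565)² / 0.09 = 32.9, so 33.

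Power at 33 per arm is 80.06%, and 66/0.9 = 73.3, so 74 randomised. The stated 66 and 74 reproduce, with almost no margin above 80%.

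**1. At-SRE test**

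Size of the subset: 33 × 0.60 = 19.8 and 33 × 0.30 = 9.9, so about 20 vs 10 if every form is returned.

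Model (assumed): each patient has a standard normal liability. An SRE occurs above the 40th percentile in control (60%) and above the 70th in the RT arm (30%). The score has correlation ρ with liability, and RT has no effect on the score. Mean liability among patients with an SRE is

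- control: φ(−0.253)/0.6 = 0.644
- RT: φ(0.524)/0.3 = 1.159

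The difference is 0.515, so the spurious arm difference is 0.515ρ SD. Rejection rates are for the two-sided 5% Wilcoxon test over 8,000 simulated trials per ρ.

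| ρ (assumed) | Spurious difference (SD) | Wilcoxon rejects |
|---|---|---|
| 0 | 0 | 4.4% |
| 0.3 | 0.15 | 6% |
| 0.5 | 0.26 | 10% |
| 0.7 | 0.36 | 17% |

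A second model, in which frailty drives both SRE and score, gave 0.13–0.28 SD and 6–11% rejection (4.6% when frailty does not drive SRE).

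**2. Baseline adjustment**

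True difference 0.5 SD, two-sided 5%. Adjusting for a baseline with correlation ρ multiplies the SD by √(1−ρ²). By normal approximation,

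power = Φ(0.5·√(n/2)/√(1−ρ²) − 1.96).

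At n = 33 per arm:
- unadjusted: Φ(2.031 − 1.96) = 52.8%
- ρ = 0.3: Φ(2.129 − 1.96) = 56.7%
- ρ = 0.5: Φ(2.345 − 1.96) = 65.0%
- ρ = 0.7: Φ(2.844 − 1.96) = 81.2%

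The noncentral t gives 51.6% vs 55.4%, 63.7% and 80.0%. Simulating the Wilcoxon test actually planned (normal scores, 20,000 trials) gives 50% vs 55%, 63% and 80%.

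For 12 months, Section 14.0 says "We expect 60-80% of the enrolled patients can be followed for 1 year". With 37 per arm that is 0.6 × 37 = 22.2 to 0.8 × 37 = 29.6, or 22–30. Over that range, Wilcoxon power is 35–45%. ANCOVA gives 39–50% (ρ = 0.3), 45–58% (0.5) and 61–75% (0.7).

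**3. Strata**

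Thirty-three per arm, one lesion per patient, two strata, and a common odds ratio of (0.3/0.7)/(0.6/0.4) = 0.286. The pooled z-test is compared with the Cochran–Mantel–Haenszel (CMH) test over 200,000 trials. Stratum rates and mix are assumed.

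| Control rates in the strata | Unadjusted power | CMH power |
|---|---|---|
| 50% / 90%, mixed 25:8 | 70.3% | 73.1% |
| 40% / 80% | 69.8% | 72.8% |
| 45% / 75% | 75.4% | 76.2% |
| 50% / 70% | 78.7% | 78.9% |
| not prognostic | 81.2% | 81.2% |

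Only the comparison within a row measures the cost of ignoring strata. Differences between rows also reflect the treated rate: in the first row it averages (25 × 0.222 + 8 × 0.720)/33 = 34%, not 30%. Holding it at 30% gives gains of 0.2–2.4 points. In the prognostic rows the unadjusted one-sided error is 3.8–4.9%, at or below nominal.

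With four equal strata and the arm averages held at 60% and 30%, power was 82.6% vs 84.4% for moderately prognostic strata. For very strong strata (control rates 20% to 93%) it was 84.9% vs 91.3%.

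Sparse strata reverse the gain. With 66 patients, assumed blocks of 4 and control rates of 50–70%, power is 80.0% unadjusted vs 77.9% CMH with 12 strata, and 80.5% vs 73.5% with 24.

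**The case against.** **Unadjusted tests are valid, and stratifying may not help.** This stands as far as it goes. The gain in the two-stratum cases is about 0–3 points, the number of levels is not stated, and a dozen or more strata would turn the gain into a loss. No calculation was made for the log-rank tests. That limits the strata point to a modest one and makes a coarse pooling rule essential.

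**The baseline gain may be overstated.** Part of the 50% to 55% step at ρ = 0.3 is the change from Wilcoxon to a linear model; against an unadjusted t-test the gain is 55.4 − 51.6 = 3.8 points. Patients enter with little or no pain, so scores may pile up near zero. With skewed, floored 0–10 scores (assumed shape, 33 per arm), Wilcoxon vs ANCOVA power was 41% vs 39% at ρ = 0.3, 42% vs 42% at 0.5 and 43% vs 54% at 0.7. So at low correlation the gain can vanish, which is a reason to keep Wilcoxon as a sensitivity analysis.

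**Follow-up may stop at an SRE.** Section 13.0 keeps patients on protocol for 12 months or until an SRE. Read literally, at most 33 × 0.4 = 13 vs 33 × 0.7 = 23 patients would give a 12-month score, themselves selected by SRE. Sections 10.0 and 14.0 can be read otherwise. This is a real ambiguity, but it harms the planned Wilcoxon tests at least as much as a mixed model.

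**The at-SRE test is secondary, optional and biased against RT.** In the model above, nearly all false rejections show RT patients worse; under 1% of trials falsely favour RT. That makes a false claim of benefit unlikely, but a misleading finding of harm is still possible.

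**Conclusion.** The concern holds on all three points, and the plan should be corrected.

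- **At-SRE test.** That it is not a randomised comparison follows from the text alone. The size, 0.15–0.36 SD and 6–17% rejection at a nominal 5%, depends on assumed correlations of 0.3–0.7.
- **Baseline scores.** The loss is roughly 5 to 30 points of power at 33 per arm with normal scores (50% vs 55–80%). It could be near zero if correlation is low and scores are floored.
- **Strata.** The loss is 0–3 points in the two-stratum cases and about 6 only with very strong strata.

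The omissions of baseline and strata do not inflate false positives. No net error rate is claimed for the per-lesion primary test, because treating lesions within a patient as independent pushes the error in the other direction. The documents give no stratum rates, levels, block size or correlations, so all of these are assumptions.

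**What to change.** 1. Report at-SRE BPI and EQ-5D-5L scores descriptively by arm, with no between-arm test.
2. Make the main questionnaire analysis a prespecified mixed model (or ANCOVA at each visit) on the 3-, 6- and 12-month scores, adjusted for baseline score and pooled strata. Keep the Wilcoxon tests as sensitivity analyses. State whether scheduled questionnaires continue after an SRE, so that Section 13.0 agrees with Sections 10.0 and 14.0.
3. Include the randomisation factors in the primary analysis as covariates in a model that also allows for lesions clustered within patients. If the analysis is reduced to one unit per patient, a CMH-type test will do.
4. Stratify the log-rank tests by the same factors.
5. Fix the pooling rule before any outcome is seen, with about 2–6 strata in total.

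The cost is SAP wording; the variables are already scheduled for collection. If follow-up in practice stops at an SRE, continuing the later questionnaires would be an added task. The real risk is over-stratifying, at about 2–7 points of power with 12–24 sparse strata, which the pooling rule is there to prevent.

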#### 16.0 DATAMANAGEMENT ISSUES

A Clinical Research Coordinator (CRC) will be assigned to the study. The responsibilities of the (CRC) include project compliance, data collection, abstraction and entry, data reporting, regulatory monitoring, problem resolution and prioritization, and coordination of activities

of the protocol study team.

The data collected for this study will be entered into the Clinical Research Database (CRDB). Source documentation will be available to support the computerized patient record.

# 16.1 Quality Assurance

An assigned (CRC) will work with the principal investigators to ensure proper adherence to the protocol, eligibility verification, informed consent and data accuracy.

Weekly registration reports will be generated to monitor patient accruals and completeness of registration data. Routine data quality reports will be generated to assess missing data and inconsistencies. Accrual rates and accuracy of evaluations and follow-up will be monitored periodically throughout the study period and potential problems will be brought to the attention of the study team for discussion and action.

Random-sample data quality and protocol compliance audits will be conducted by the study team, at a minimum of two times per year, more frequently if indicated.

# 16.2 Data and Safety Monitoring

With the help of the CRC, the principal investigator will review each case at the time of enrollment to verify eligibility. The CRC will work with the principal investigator to ensure that the protocol is followed carefully.

The Data and Safety Monitoring (DSM) Plans at Memorial Sloan Kettering Cancer Center were approved by the National Cancer Institute in September 2001. The plans address the new policies set forth by the NCI in the document entitled "Policy of the National Cancer Institute for Data and Safety Monitoring of Clinical Trials" which can be found at: http://cancertrials.nci.nih.gov/researchers/dsm/index.html. The DSM Plans at MSKCC were established and are monitored by the Office of Clinical Research. The MSKCC Data and Safety Monitoring Plans can be found on the MSKCC Intranet at: http://mskweb2.mskcc.org/irb/index.htm.

Page **24** of **30** Version: 2/26/16

There are several different mechanisms by which clinical trials are monitored for data, safety and quality. There are institutional processes in place for quality assurance (e.g., protocol monitoring, compliance, and data verification audits, therapeutic response, and staff education on clinical research QA) and department procedures for quality control. In addition, there are two institutional committees that are responsible for monitoring the activities of our clinical trials programs. The committees, including the *Data and Safety Monitoring Committee (DSMC)* for phase I and II clinical trials, and the *Data and Safety Monitoring Board (DSMB)* for Phase III clinical trials, report to the Center's Research Council and Institutional Review Board.

During the protocol development and review process, each protocol will be assessed for its level of risk and degree of monitoring required. Every type of protocol (e.g., NIH sponsored, in-house sponsored, industrial sponsored, NCI cooperative group, etc.) will be addressed and the monitoring procedures will be established at the time of protocol activation

Page **25** of **30** Version: 2/26/16

#### 17.0 PROTECTION OF HUMAN SUBJECTS

Every effort will be made to protect the rights of human subjects per institutional policy. A full discussion of the risks, benefits, expected toxicities, alternatives and treatment options will be undertaken. No additional financial costs or burdens will result as a consequence of joining the study. Informed consent is a prerequisite for enrollment on the study.

In accordance with institutional policy, privacy and confidentiality of medical records will be strictly observed. All data pertaining to the study will also be protected. The study is entirely voluntary. Patients who do not wish to participate in the study will be offered all treatment options including those considered to be the standard of care.

# 17.1 Privacy

MSK"s Privacy Office may allow the use and disclosure of protected health information pursuant to a completed and signed Research Authorization form. The use and disclosure of protected health information will be limited to the individuals described in the Research Authorization form. A Research Authorization form must be completed by the Principal Investigator and approved by the IRB and Privacy Board (IRB/PB).

The consent indicates that individualized de-identified information collected for the purposes of this study may be shared with other qualified researchers. Only researchers who have received approval from MSK will be allowed to access this information which will not include protected health information, such as the participant's name, except for dates. It is also stated in the Research Authorization that their research data may be shared with other qualified researchers.

## 17.2 Serious Adverse Event (SAE) Reporting

An adverse event is considered serious if it results in ANY of the following outcomes:

- Death
- A life-threatening adverse event
- An adverse event that results in inpatient hospitalization or prolongation of existing hospitalization
- A persistent or significant incapacity or substantial disruption of the ability to conduct normal life functions
- A congenital anomaly/birth defect
- Important Medical Events (IME) that may not result in death, be life threatening, or require hospitalization may be considered serious when, based upon medical judgment, they may jeopardize the patient or participant and may require medical or surgical intervention to prevent one of the outcomes listed in this definition

Note: Hospital admission for a planned procedure/disease treatment is not considered an SAE.

Page **26** of **30** Version: 2/26/16

SAE reporting is required as soon as the participant starts investigational treatment/intervention. SAE reporting is required for 30-days after the participant"s last investigational treatment/intervention. Any events that occur after the 30-day period that is unexpected and at least possibly related to protocol treatment must be reported.

Page **27** of **30** Version: 2/26/16

Please note: Any SAE that occurs prior to the start of investigational treatment/intervention and is related to a screening test or procedure (i.e., a screening biopsy) must be reported.

All SAEs must be submitted in PIMS. If an SAE requires submission to the HRPP office per IRB SOP RR-408 'Reporting of Serious Adverse Events', the SAE report must be submitted within 5 calendar days of the event, All other SAEs must be submitted within 30 calendar days of the event.

The report should contain the following information:

- The date the adverse event occurred
- The adverse event
- The grade of the event
- Relationship of the adverse event to the treatment(s)
- If the AE was expected
- Detailed text that includes the following
  - An explanation of how the AE was handled
  - o A description of the participant's condition
  - Indication if the participant remains on the study
- If an amendment will need to be made to the protocol and/or consent form
- If the SAE is an Unanticipated Problem

